5. STATISTICAL METHODS

All data including both safety and efficacy will be summarized overall for all patients in SAF.

For continuous variables, descriptive statistics will include the following: the number of patients reflected in the calculation (n), mean, median, Q1 (25% percentile), Q3 (75% percentile), standard deviation, minimum, and maximum.

For categorical or ordinal data, frequencies and percentages will be displayed for each category.

5.1. Demographics and Baseline Characteristics

5.1.1. Demographics and Baseline Characteristics of Current Study

The following demographics and baseline characteristics of current study as specified in Section 4.1 will be summarized overall for all patients in SAF.

- Demographics,
- Baseline characteristics in current study

5.1.2. Characteristics in Parent Study

The following demographics and baseline characteristics from the parent study as specified in Section 4.2 will be summarized overall for all patients in SAF.

- Baseline characteristics in parent study,
- End of treatment status of a patient in the parent study,
- Duration of off treatment period (days) before baseline
- Duration of patient exposure to dupilumab in the parent study

5.2. General Medical History and AD History

Medical history in current study will be summarized by primary SOC and PT. The table will be sorted by decreasing frequency of SOC followed by PT. Medical history will be listed.

AD medical history will be summarized by number and percentage of patients with each type of AD medical history.

5.3. Pre-treatment/Concomitant Medications/Procedures

Number and proportion of patients taking prior/concomitant medication will be summarized, sorted by decreasing frequency of ATC Level 2 and ATC level 4. Patients will be counted only once for each medical class (ATC level 2 and 4) linked to the medication.

Listing of pre-treatment medication and concomitant medications will include generic name and ATC levels 2 and 4, indication, study day onset (for medications started before treatment, the study day onset (defined as date of medication start - date of the first dose; for medications started on or after treatment, the study day onset = date of medication start - date of the first dose+1), the study end date (defined similarly as for study onset day), ongoing status, dose, frequency, route.

5.4. Subject Disposition

The following summaries by table will be provided for all patients in SAF:

- The total number of screened patients
- The total number of enrolled patients
- The total number of patients enrolled and reconsented under each protocol amendment
- The total number of patients in each analysis set
- The total number of patients who completed the study including a summary of patients who completed the study under each protocol amendment, completed up to week 52, completed up to week 100, complete up to week 148, completed up to week 156, completed up to week 208, completed up to week 260, and completed up to week 272
- The total number of patients who discontinued the study and the reasons for discontinuation
- The total number of patients who completed study treatment including a summary of patients who completed treatment under each protocol amendment
- The total number of patients who discontinued the study treatment and the reasons for discontinuation
- The total number of patients who discontinued the study, and the reasons for discontinuation cumulatively by visits (i.e. end of week 1, end of week 2, end of week 4, end of week 8, end of week 12, end of week 16, end of week 24, end of week 36, end of week 48, end of weeks 52, end of week 76, end of week 100, end of week 124, end of week 148, end of week 164, end of week 208, end of week 260, end of study). The visits in weeks are categorized based on study days from the first dose date in current study. For example, end of week 1 corresponds to study day 8.

As patients from different countries can have different study duration and treatment duration according to the country specified protocol amendment, subgroup analysis of the disposition data by country of interest will be provided.

The following listings will be provided:

- Listing of subject disposition including: date of enrollment, date of the last visit, received dose, completed study or discontinued by reason, a flag indicating if a patient completed study under protocol amendment 6 then retry into study under protocol amendment 7
- A listing of patients enrolled but not treated
- A listing of patients prematurely discontinued from the study or treatment, along with reasons for discontinuation, summary tables of reasons will be provided
- A listing and a summary table of major protocol deviations will be provided

5.5. Dupilumab Dose administration

The compliance with protocol-defined investigational product will be calculated as follows:

Treatment Compliance= (Number of injections during exposure period) / (Number of planned injections during exposure period) x 100%

Loading doses for the same patient will be counted as 1.

Treatment compliance will be calculated and summarized for the following periods of interest.

- Overall study treatment period
- The treatment period prior to “treatment gap” (defined below)

As shown in [Figure 1](#) of Section 2.3, due to the implementation of protocol amendments 7 and 8, patients in certain countries experienced a gap in treatment between completion of the treatment period under a prior protocol amendment and the beginning of a new protocol amendment. Specifically, there are two types of treatment gaps:

- Patients from Germany, France, Poland and Japan who completed the 3-year treatment period under protocol amendment 6, and resumed dupilumab treatment after reconsenting to amendment 7.
- Patients from Poland, Finland and France who completed the treatment period under protocol amendment 7 and resumed treatment after reconsenting to protocol amendment 8.

- The “continuous-treatment” period (defined below)
For the QW regimen being evaluated in this study, the decline in concentrations of dupilumab following an interruption in treatment of ≤ 8 weeks is not expected to be sufficient to have a substantial impact on the pharmacodynamic effect of dupilumab. For patients with a treatment gap ≤ 8 weeks, a “continuous-treatment” period is defined as the combined prior to “treatment gap” period and “post-gap” period. For patients who did not consent to protocol amendment 7 or 8, the “continuous-treatment” period is the study treatment period.
- The treatment extension period under protocol amendment 7 for patients from Germany, Poland, France and Japan who completed 3-year treatment
- The treatment extension period under protocol amendment 8 for patients from Poland, Finland and France who consent to protocol amendment 8

Treatment compliance during both “treatment extension” periods will be summarized. Number of patient with each type of gap in treatment and duration of gap will be summarized.

Summary of study drug administration will include the number of study drug doses administered, and treatment compliance. The treatment compliance will be presented by the following specific ranges: $<80\%$, and $\geq 80\%$.

Listing of dose administration: including date/time, study day, number of injections, locations of injections and dosing information will be presented.

5.6. Treatment Exposure and Observation Period

The duration of treatment exposure period during the study in week is calculated as:

$$[(\text{Date of last study drug injection} - \text{date of first study drug injection}) + 7]/7$$

regardless of unplanned intermittent discontinuations. For the exposure calculation, the two treatment gaps due to patients resuming treatment under protocol amendment 7 or 8 will be excluded. The duration of exposure will be summarized using number of patients, means, SD, minimums, medians, and maximums. A summary of the number of doses will also be provided.

The duration of observation period during the study in weeks is calculated as:

$$[(\text{Date of the last visit} - \text{date of the first study medication dose}) + 1]/7.$$

For the duration of observation period calculation, the study gap for patients who have completed the study under protocol amendment 6 then retry into the study under protocol amendment 7 will be excluded.

The duration of observation periods will be summarized using number of patients, means, SD, minimums, medians, and maximums. The number (%) of patients with observation periods will be presented by specific time periods. The time periods of interest are specified as: ≥ 1 week, ≥ 4 weeks, ≥ 12 weeks, ≥ 16 weeks, ≥ 24 weeks, ≥ 52 weeks, ≥ 76 weeks, ≥ 100 weeks, ≥ 104 weeks, ≥ 124 weeks, ≥ 148 weeks, ≥ 156 weeks, ≥ 164 weeks, ≥ 208 weeks, ≥ 260 weeks, ≥ 272 weeks.

As of protocol amendment 2, the weekly dose of dupilumab was changed from 200 mg to 300 mg. The number of patients exposed to 200 mg dose, the number of 200 mg doses and duration of treatment exposure with 200 mg and 300 mg in weeks will be calculated and summarized separately.

[Appendix 10.10](#) provides the detailed algorithm for calculating duration of treatment exposure and observational period.

5.7. Analyses of Efficacy Variables

The efficacy variables will be summarized for all patients in SAF. The continuous efficacy variables will be summarized using number of patients, means, SD, minimums, medians, Q1, Q3 and maximums. Categorical efficacy variables will be summarized using patient counts and proportion. No formal statistical hypothesis testing will be performed. The graph of mean value for continuous variable or proportion for categorical variable by visit will be provided.

All observed values, regardless of whether rescue treatment is used or data is collected after withdrawal from study treatment will be used for analysis. No missing values will be imputed.

For the categorical efficacy variables, the proportion of patients with each response at each visit will be calculated using the number of patients with a non-missing value at the visit as the denominator.

As described in Section 5.6, there are up to two potential “treatment gaps” due to patient re-entry to the study for protocol amendments 7 and 8 for patients from Germany, France, Poland and Japan. The primary focus of the efficacy data will be on the data collected prior to these potential “treatment gaps”.

- If the “treatment gap” is ≤ 8 weeks, then all efficacy data will be summarized together, i.e. data will be analyzed as if the patient had been dosed continuously
- If the “treatment gap” is > 8 weeks, efficacy data collected before and after the treatment gap will be summarized separately.

Data collected under end of study visit (i.e. off-treatment measurement at the end of 12-week or 16-week safety follow up period) will be summarized separately from the data while the patient was on treatment.

For the analysis of Pruritus NRS, the weekly NRS collected during the safety follow-up period, during the treatment gap between amendments 6 and 7, and between amendments 7 and 8 will be separated from the NRS collected during treatment. The primary focus of NRS data will be on the data collected during treatment.

Subgroup analyses for efficacy

Different subgroups within the overall SAF population will be defined as below. The analyses will be performed for the secondary efficacy variables related to EASI, IGA and pruritus NRS by:

- Duration of AD at Day 1 of current study (< 26 years, ≥26 years)
- Baseline body weight of current study ((<70 kg, ≥70-<100 kg, ≥100 kg)
- Baseline BMI of current study (<15, [15-25), [25-30), ≥30)
- Age (≥18-<40, ≥40-<65, ≥65)
- Gender (Male, Female)
- Race (White, Black or African American, Asian, Others)
- Ethnicity: Hispanic or Latino (yes/no)
- Previous usage of ciclosporin (CsA) (Yes, No)
- Previous usage of methotrexate (MTX) (Yes, No)
- Previous usage of Azathioprine (Aza) (Yes, No)
- Previous use of systemic immunosuppressants for AD (Yes, No)
- History of asthma (Yes, No)
- History of nasal polys (Yes, No)
- History of allergic rhinitis (Yes, No)
- History of food allergies (Yes, No)
- Previous treatment of dupilumab in parent study (Yes, No)
 - For patients who received dupilumab in parent study, data from the following two subgroups will also be summarized.
 - Re-treatment (treatment gap > 8 weeks): – Patients who came from the dupilumab arms of parent studies, and if the gap period between the last dupilumab study drug injection in parent study and the first study drug injection in current study is > 8 weeks (greater than 64 days).
 - Continuous treatment (gap ≤ 8 weeks) – patients who came from the dupilumab arms of parent studies, and if the gap period between the last dupilumab study drug injection in parent study and the first study drug injection in current study is ≤ 8 weeks (less than or equal to 64 days).

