#### 5.2.2.1. Reasons for Permanent Discontinuation of Study Drug

Patients will be permanently discontinued from study drug dosing in the event of:

- Anaphylactic reaction or other severe systemic reaction to study drug
- Diagnosis of a malignancy during study, excluding carcinoma in situ of the cervix, or squamous or basal cell carcinoma of the skin
- Pregnancy at any time during the study
- Any infection that is opportunistic, such as active tuberculosis and other infections whose nature or course may suggest an immuno-compromised status
- Severe laboratory abnormalities that are judged to be related to dupilumab per criteria described in Section 7.3.2, such as:
  - Neutrophil count  $\leq 0.5 \times 10^3/\mu\text{L}$
  - Platelet count  $\leq 50 \times 10^3/\mu\text{L}$
  - Confirmed (by 2 separate tests at least 2 weeks apart) alanine aminotransferase (ALT) and/or aspartate aminotransferase (AST) values  $>3 \times$  upper limit of normal (ULN) and total bilirubin  $>2 \times$  ULN, excluding confirmed Gilbert's Syndrome
  - Confirmed AST and/or ALT  $>5 \times$  ULN (for more than 2 weeks)
- Inadequate efficacy:
  - Patients who show inadequate therapeutic response after at least 12 weeks of treatment with dupilumab will be discontinued from the study treatment based upon review of the case and joint decision by the investigator and medical monitor. For the purpose of this assessment, a review of efficacy will be triggered whenever patients fail to achieve and/or maintain EASI-25 (at least 25% improvement in the EASI score) at week 16, compared to the baseline score in the previous controlled and/or short-term study. Patients may also withdraw from the study at any time if they are not satisfied with the study treatment (see Section 4.3)
- Other reasons that may lead to the permanent discontinuation of study drug include:
  - Certain AEs deemed related to the study drug (eg, severe and prolonged ISRs)

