4.5. Efficacy Variables

Analysis of efficacy variables will be performed in the overall SAF population, as described in Section 3.1.

Starting from protocol amendment 6, the following assessments were removed from the schedule of events. All available data collected prior to implementation of protocol amendment 6 will still be summarized.

- POEM
- Dermatology Life Quality Index (DLQI)
- EQ-5D
- Patient Global Assessment of Disease Status
- Patient Global Assessment of Treatment Effect

All efficacy related endpoints for this study are secondary endpoints. Secondary endpoints include:

- Key secondary endpoints
 - Proportion of patients with IGA score of either 0 or 1 at each visit
 - Proportion of patients with EASI-75 relative to baseline of parent study ($\geq 75\%$ reduction in EASI scores from baseline of parent study) at each visit
- Other secondary endpoints
 - Proportion of patients with low disease activity state (ie., IGA ≤ 2) at each visit
 - Proportion of patients achieving an IGA reduction of ≥ 2 from Day 1 of current study at each visit for patients with Day 1 IGA score of current study ≥ 2
 - Percentage change from Day 1 of current study in EASI score at each visit
 - Percentage change from baseline of parent study in EASI score at each visit
 - Change from Day 1 of current study in EASI score at each visit
 - Change from baseline of parent study in EASI score at each visit
 - Proportion of patients with EASI-50 relative to baseline of parent study ($\geq 50\%$ reduction in EASI scores from baseline of parent study) at each visit
 - Proportion of patients with EASI-90 relative to baseline of parent study ($\geq 90\%$ reduction in EASI scores from baseline of parent study) at each visit
 - Percent change from Day 1 of current study in pruritus NRS at each week
 - Percent change from baseline of parent study in pruritus NRS at each week
 - Change from Day 1 of current study in pruritus NRS at each week
 - Change from baseline of parent study in pruritus NRS at each week
 - Proportion of patients with improvement (reduction) of pruritus NRS ≥ 4 from Day 1 of current study or achieving NRS score of 0 at each visit
 - Proportion of patients with improvement (reduction) of pruritus NRS ≥ 4 from baseline of parent study or achieving NRS score of 0 at each visit
 - Proportion of patients with improvement (reduction) of pruritus NRS ≥ 3 from Day 1 of current study or achieving NRS score of 0 at each visit

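### IGA 0-1 and EASI-75 at each visit are computed only among patients with a value, so patients stopped for inadequate response leave later denominators; later response is likely overstated and no supportive analysis shows by how much

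*SAP*

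**What the plan says.** SAP 4.5 names two efficacy endpoints as key secondary: "Proportion of patients with IGA score of either 0 or 1 at each visit" and "Proportion of patients with EASI-75 relative to baseline of parent study", the latter also at each visit. SAP 5.7 gives the rule for both. Each proportion is calculated "using the number of patients with a non-missing value at the visit as the denominator", and "No missing values will be imputed". Values after rescue or after stopping treatment are kept if they exist: "All observed values, regardless of whether rescue treatment is used or data is collected after withdrawal from study treatment will be used for analysis". End of study data are summarised apart from on-treatment data, and a graph of the proportions by visit is planned. Appendix 10.1 enters No under supportive method for both continuous and categorical efficacy variables.

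Protocol 5.2.2.1 makes staying on treatment depend partly on response. Patients with an inadequate response after at least 12 weeks "will be discontinued from the study treatment based upon review of the case and joint decision by the investigator and medical monitor". For that purpose, "a review of efficacy will be triggered whenever patients fail to achieve and/or maintain EASI-25" at week 16, relative to the baseline of the previous study. The same paragraph adds: "Patients may also withdraw from the study at any time if they are not satisfied with the study treatment".

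Patients who stop permanently are asked for an early termination visit and an end of study visit 12 weeks after the last dose (Protocol 5.2.2, 5.5.2, 6.2.7 and 6.2.8). No further on-treatment efficacy visits are scheduled for them.

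**The concern.** Whether a patient has a value at a later visit is partly decided by how well the patient responded earlier. An observed-case proportion then describes the patients who remain, not all those who started. The planned graph by visit invites the second reading.

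The SAP's use of post-withdrawal data does not repair this, because almost none are scheduled. SAP 5.4 does plan reasons for study discontinuation, cumulative by visit, but no table joins those counts to the response denominators. A reader of the two efficacy key secondary endpoints would see a likely overstated figure without a companion figure showing how much depends on who left.

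**Working it through.** The documents state no expected response rate, no dropout rate and no sample size calculation (Protocol 9.2, SAP 2.2). There is therefore no planned figure to reproduce. The check has two parts: whether stopped patients really leave the denominators, and how large the effect could be.

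**1. Following one stopped patient.** Week 16 is day 113. Suppose the review leads to stopping and an early termination visit on day 141 (an assumed date).
- SAP 6.4 maps early termination values by study day. Day 141 lies in the window 128 to 155, labelled week 20, a visit that Amendment 6 removed.
- If the last dose was on day 113, the end of study visit is due on day 113 + 84 = 197. SAP 5.7 summarises it separately. Even if it were mapped by study day, it would fall in the week 28 window (184 to 211).
- In the current schedule the next IGA/EASI after week 16 is at week 48 (window 324 to 351), then weeks 60, 100, 124, 156 and 204.

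This patient contributes to none of those denominators.

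**2. Size.** Let p_obs be the observed response at a visit, and d the share of patients due at that visit who have stopped for a response-related reason and have no value. Counting them as non-responders gives

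p_adj = p_obs × (1 − d), a reduction of p_obs × d.

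Both inputs are assumptions. Applied to the 2678 enrolled (SAP 2.2), d from 2% to 15% would be 54 to 402 patients.

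| p_obs | d = 2% | d = 5% | d = 10% | d = 15% |
|---|---|---|---|---|
| 60% | 58.8% | 57.0% | 54.0% | 51.0% |
| 70% | 68.6% | 66.5% | 63.0% | 59.5% |
| 80% | 78.4% | 76.0% | 72.0% | 68.0% |

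The reduction runs from 0.60 × 0.02 = 1.2 points to 0.80 × 0.15 = 12.0 points.

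**3. The review is not automatic.** If 10% fail EASI-25 and the review stops half of them, d = 5% and 80% becomes 0.80 × 0.95 = 76.0%. If it stops none, the figure stays at 80.0%.

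**4. Why not count every missing value as failure.** With a share m missing for any reason, the response lies between p_obs × (1 − m) and p_obs × (1 − m) + m. For an observed 80% this is 72% to 82% at m = 10%, 56% to 86% at 30%, and 40% to 90% at 50%. SAP Table 2 ends treatment at week 148 or at commercial availability in many countries, so much late missingness is administrative. The lower bound would be far too severe.

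**5. Why the cut-off must be common.** Take 1000 patients (assumed). Of these, 100 stop and 900 continue; half of the 900 leave administratively, and 80% of the remaining 450 respond, which is 360.
- If the 100 stay in as failures: 360 / (450 + 100) = 65.5%.
- If half of the 100 also leave at the same administrative point: 360 / (450 + 50) = 72.0%, which equals 0.80 × 0.90.

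Without a common cut-off, failures accumulate and the supportive figure errs in the other direction.

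**The case against.** The strongest case against acting is that this is a single-arm safety study. Efficacy is secondary and descriptive, there is no hypothesis (Protocol 9.1), and Protocol 9.5.3 itself prescribes analysis of all observed data. The observed-case table follows the protocol and is not an error. That stands, and it is why the table should remain the main analysis.

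Second, a reader could combine the planned response table with the cumulative discontinuation table in SAP 5.4, which is also planned by country of interest, and approximate the reduction. This stands only in part. The by-visit table counts study discontinuations, whereas the Protocol 5.2.2.1 review stops study treatment. It also does not say how many stopped patients would still have been due at a given visit.

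Third, an early termination value can enter one analysis window, so a failing patient may be counted once. True, but step 1 of the check shows that this need not be a visit at which others are assessed, and it never carries forward.

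Fourth, exits for commercial availability or country end dates may be unrelated to response, or may even favour responders. This stands. Only response-related exits push the figure up, so the overall direction is expected rather than shown.

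**Conclusion.** The point holds as an inexpensive improvement. The denominator rule, the response-related exits, the absence of later scheduled visits and the empty supportive column are all documented. Together they make later-visit IGA 0-1 and EASI-75 likely overstated by p_obs × d. The actual size is unknown. The example of 80% falling to 76% or 72% rests on assumed exits of 5% or 10%, all counted as non-response.

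Four stronger readings may occur to a reader, and the documents do not support them.
- **That every week-16 EASI-25 failure is removed.** Failure triggers a review and a joint decision, and what stops is study treatment.
- **That SAP 4.2 uses the opposite convention on the same curve, because missing parent-study status counts as non-response.** That variable describes patients at entry (SAP 5.1.2) and is defined after censoring for rescue. It is not a point on this study's by-visit curve, which uses observed values throughout.
- **That a curve rising over 3 to 5 years would be an artefact.** The EASI-25 trigger is tied to week 16. It can shift the level afterwards but does not by itself produce a continuing rise. Under the SAP's protocol versions, treatment up to 5 years applied only in Poland and Finland.
- **That the effect could be 18 points.** This needs an observed 90% together with 20% exits (0.90 × 0.20), and the documents give neither.

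**What to change.** Keep the observed-case table and graph as the main analysis. In the next SAP revision or addendum (Protocol 9 and SAP 7 both allow for one), add to SAP 5.7 and Appendix 10.1 a supportive line for IGA 0-1 and EASI-75 at each scheduled IGA/EASI visit:

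1. Patients who stopped for lack of efficacy, an AE or dissatisfaction count as non-responders at visits after they stopped. Say plainly that this is a treatment-failure convention, not an estimate of what they would have scored.
2. One administrative cut-off applies to everyone. Stopped and continuing patients alike leave the denominator at the visit where commercial availability or the country end date would have ended their treatment.
3. Show n/N at each visit, with exits by reason beside it.

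Reasons for stopping treatment and study are already to be tabulated under SAP 5.4. Two details need settling in advance. One is the cut-off date per country or region where SAP Table 2 gives only commercial availability. The other is which disposition codes count as dissatisfaction, since the documents do not list the codes. The cost is one extra table, those two definitions, and a supportive figure less favourable than the observed one. No data collection or clinical rule changes.
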